6.3 Study Visits and Procedures

For each subject, approximately 10 visits will be performed: screening visit, baseline visits for each treatment period, 2 weekly phone visits plus a Day 21 clinic visit during each treatment period, and an off-treatment safety follow-up visit after each treatment period. The subject will undergo assessments for Follow-Up Visit of Treatment Period 1 and the Baseline Visit for Treatment Period 2 on the same calendar day. The procedures and assessments to be performed during each period/time point are indicated in the Schedule of Events (*Table 1* and *Table 2*). Further relevant details of the evaluations to be performed at each visit are described below.

6.3.1 Treatment Period 1

Screening Visit 1 (Day -45 to Day -2)

Up to 44 days prior to randomization, subjects will participate in a screening visit to determine eligibility to proceed in the study.

Subjects may be re-screened at the discretion of the Medical Monitor and with written permission from the Sponsor. In cases of other unique circumstances that may justify re-screening, Investigators must contact the Medical Monitor to discuss the specific conditions under which subjects may qualify for re-screening.

During screening, subjects will provide informed consent and undergo the following assessments and procedures:

- Review of eligibility/inclusion and exclusion criteria
- Demographics and medical history
- Physical examination
- Height, weight, and body mass index
- ECG (triplicate)
- Measurement of vital signs (blood pressure, heart rate, and respiratory rate), body temperature and pulse oximetry
- Spirometry
- DLco measurement (within the previous 6 months or approval of medical monitor)
- Swallow test
- Cough Severity Numerical Rating Scale (administered on paper at screening)
- Clinical laboratory testing (chemistry, hematology, urinalysis, and coagulation)
- Serum and urine pregnancy testing (females of childbearing potential)
- Contraceptive counseling (if applicable)
- Dispense Subject Medication and Symptom Log

• Record and assess adverse events, concomitant medications, and therapies (including restricted and prohibited medications)

Baseline Visit 2 (Day -1)

Subjects will return for the baseline visit, at which point it will be determined if they meet all study entry criteria prior to being randomized. Subjects will undergo the following assessments during this visit:

- Confirm eligibility against inclusion/exclusion criteria
- Urine pregnancy tests (females of childbearing potential)
- Contraceptive counseling (if applicable)
- Cough Severity Numerical Rating Scale
- Fatigue Scale (Short Form 7a)
- Review and re-dispense Subject Medication and Symptom Log
- Randomization via Interactive Voice/Web Response System (IVRS/IWRS)
- Dispense investigational product blister card
- Provide subject with dosing instructions including instructions for recording daily dosing
- Dispense e-diary and train on its use
- Provide instructions for completing the EXACT version 1.1 e-diary tool
- Dispense cough monitor, train subject on use and provide instruction for removing the device prior to bedtime and prior to taking the first dose of investigational product the next day (Day 1)
- Provide packing and shipping materials for return of cough monitor to Vitalograph® after removal
- Record and assess adverse events, concomitant medications, and therapies (including restricted and prohibited medications)

Telephone Visit 3 and 4 (Day 8 and 15)

Visit 3 (Day 8) and Visit 4 (day 15) will be performed via a telephone call to the Subject. During these visits, subjects will undergo the following assessments:

- Contraceptive counseling (if applicable)
- Cough Severity Numerical Rating Scale
- Review e-diary entries with subjects for compliance, and re-train on use of e-diary if needed
- EXACT version 1.1 e-diary tool and reminder to complete it daily until the next visit
- Review Subject Medication and Symptom Log with subject
- Review blister card accountability/compliance with subject
- Record and assess adverse events, concomitant medications, and therapies (including restricted and prohibited medications)

Treatment Visit 5 (Day 21)

During this visit, subjects will undergo the following assessments:

- Spirometry
- Clinical laboratory testing (chemistry, hematology, urinalysis, and coagulation)
- PK blood sampling
- Contraceptive counseling (if applicable)
- Cough Severity Numerical Rating Scale
- Fatigue Scale (Short Form 7a)
- CGI-C
- Review e-diary entries for compliance, and re-train on use of e-diary if needed
- EXACT version 1.1 e-diary tool and reminder to complete it daily until end of treatment
- Dispense cough monitor, train subject on use and provide instruction for removing the device prior to bedtime the next day (Day 22)
- Provide packing and shipping materials for return of cough monitor to Vitalograph® after removal
- Retrieve, review and re-dispense Subject Medication and Symptom Log
- Collect the investigational product blister card, assess accountability/compliance and return investigational product blister card to subject
- Reminder to take the final dose of investigational product on the morning of the next day (Day 22)
- Instructions for completing the Subjective Opiate Withdrawal Scale (SOWS) daily by e-diary for 14 days (beginning Day 23).
- Record and assess adverse events, concomitant medications, and therapies (including restricted and prohibited medications)

Follow-up Visit 6 (Day 36)

Subjects will return for Follow-up Visit 6 (Day 36) 14 days (+/- 2 days) after the last day of dosing in Treatment Period 1. Subjects will undergo the following assessments:

- Brief physical examination
- ECG (triplicate)
- Measurement of vital signs (blood pressure, heart rate, and respiratory rate), body temperature, and pulse oximetry
- Urine pregnancy test (females of childbearing potential)
- Collect the investigational product blister card and assess accountability/compliance
- Retrieve e-diary
- Retrieve and review Subject Medication and Symptom Log

• Record and assess adverse events, concomitant medications, and therapies (including restricted and prohibited medications)

Before proceeding to Treatment Period 2, females of childbearing potential should have a confirmed negative urine pregnancy test administered by study staff. In most instances, the Baseline visit for Treatment Period 2 will occur on the same calendar day as the Follow-up Visit 6.

6.3.2 Treatment Period 2

Baseline Visit 6 (Day -1)

The Baseline visit for Treatment Period 2 will be completed prior to Day 1 dose administration. Subjects will undergo the following assessments:

- Clinical laboratory testing (chemistry, hematology, urinalysis, and coagulation)
- Serum pregnancy test (females of childbearing potential)
- Contraceptive counseling (if applicable)
- Cough Severity Numerical Rating Scale
- Fatigue Scale (Short Form 7a)
- Re-distribute e-diary to subject, review entries for compliance, and re-train on use
- EXACT version 1.1 e-diary tool and reminder to complete it daily until the next visit
- Dispense cough monitor, re-train subject on use and provide instruction for removing the device prior to bedtime and prior to taking the first dose of investigational product the next day (Day 1)
- Provide packing and shipping materials for return of cough monitor to Vitalograph® after removal
- Dispense investigational product as per IVRS/IWRS
- Provide subject with dosing instructions
- Dispense Subject Medication and Symptom Log
- Record and assess adverse events, concomitant medications, and therapies (including restricted and prohibited medications)

Telephone Visit 7 and 8 (Day 8 and 15)

Visit 7 and 8 (Day 8 and 18) will be performed via a telephone call to subjects. During these visits, subjects will undergo the following assessments:

- Contraceptive counseling (if applicable)
- Cough Severity Numerical Rating Scale
- Review e-diary entries with subject for compliance, and re-train on use of e-diary if needed
- EXACT version 1.1 e-diary tool and reminder to complete it daily until the next visit

- Review Subject Medication and Symptom Log with subject
- Review investigational product accountability/compliance with subject
- Record and assess adverse events, concomitant medications, and therapies (including restricted and prohibited medications)

Treatment Visit 9 (Day 21)

During this visit, subjects will undergo the following assessments:

- Spirometry
- Clinical laboratory testing (chemistry, hematology, urinalysis, and coagulation)
- PK blood sampling
- Contraceptive counseling (if applicable)
- Cough Severity Numerical Rating Scale
- Fatigue Scale (Short Form 7a)
- CGI-C
- Review e-diary entries for compliance, and re-train on use of e-diary if needed
- EXACT version 1.1 e-diary tool and reminder to complete it daily until end of treatment
- Dispense cough monitor, train subject on use and provide instruction for removing the device prior to bedtime the next day (Day 22)
- Provide packing and shipping materials for return of cough monitor to Vitalograph® after removal
- Review and re-dispense Subject Medication and Symptom Log
- Collect investigational product blister card, assess accountability/compliance and return investigational product blister card to subject
- Reminder to take the final dose of investigational product on the morning of the next day (Day 22)
- Instructions for completing the SOWS daily by e-diary for 14 days (beginning Day 23).
- Record and assess adverse events, concomitant medications, and therapies (including restricted and prohibited medications)

Follow-up Visit 10 (Day 36)

Subjects will return for Follow-up Visit 10 (Day 36) 14 days (+/- 2 days) after the last day of dosing in Treatment Period 2. Subjects will undergo the following assessments:

- Brief physical examination
- ECG (triplicate)
- Measurement of vital signs (blood pressure, heart rate, and respiratory rate), body temperature, and pulse oximetry

- Urine pregnancy test (females of childbearing potential)
- Collect investigational product blister card and assess investigational product accountability/compliance.
- Retrieve e-diary
- Retrieve and review Subject Medication and Symptom Log
- Record and assess adverse events, concomitant medications, and therapies (including restricted and prohibited medications)

6.3.3 **Premature Discontinuation Visit**

Subjects who complete investigational product treatment through the full study treatment course are considered to have completed treatment (even if some doses have been missed). Subjects who discontinue investigational product prior to Treatment Period 2 (Visit 10) will be considered to have prematurely discontinued and will be asked to complete the following visits (unless consent is withdrawn):

- If the decision to discontinue treatment is made during an onsite study visit (scheduled or unscheduled), perform the procedures and assessments outlined in the Premature Discontinuation Visit, regardless of where they are in the study visit schedule.
- If the decision to discontinue treatment is made while the subject is not at a study visit, schedule a visit as soon as possible, but no later than 2 weeks later, to perform the procedures and assessments described in the Premature Discontinuation Visit. Upon notification that the subject has permanently stopped dosing, the site should instruct the subject to begin entering their SOWS data daily via the e-diary.
- The subject should be scheduled to return to the clinic 2 weeks after completion of the Premature Discontinuation Visit for procedures and assessments outlined in the Follow-up Visit (Visit 6 if in Treatment Period 1 and Visit 10 if in Treatment Period 2).

6.3.4 Unscheduled Visits

Should there be a need for an unscheduled visit or assessment (e.g., to manage or follow any unresolved adverse events), the Investigator should use his/her judgment and perform an adequate evaluation of the subject. Vital signs, physical examination, clinical laboratory tests, or any other evaluations required to assess the subject's status should be performed as clinically necessary with data recorded in the Unscheduled Visit section of the electronic Case Report Form (eCRF).

6.4 Rationale for Study Design and Dose Selection

This study has been designed as a Phase 2, double-blind, randomized, placebo-controlled, 2 treatment, 2-period crossover study of NAL ER tablets for the treatment of cough in subjects with IPF. Subjects will receive investigational product for 22 days duration during each period of the crossover. The 2 crossover treatment periods will be separated by a 2-week washout period. The published medical literature including the work of *Bacci et al (2018)* concluded that reduction

in daytime cough frequency may be the most relevant clinical endpoint for assessing the efficacy of drug effect in IPF-related cough. Daytime cough is defined as cough that occurs between the time that the subject wakes up and the time that the subject goes to bed.

The primary study endpoint, mean change in daytime cough frequency (coughs per hour), will be analyzed by use of an objective digital recording device, as consistent with the recommendations of *Boulet et al (2015)* who summarized the CHEST Expert Panel recommendations regarding tools to be used in clinical trials assessing cough. The Panel recommended that acoustic cough counting to assess cough frequency should be done through objective means. Secondarily, as supported by the development work of *Bacci et al (2018)*, the E-RS daily diary will be used as a validated patient-reported outcomes (PRO) instrument in assessing NAL ER tablets efficacy in reducing IPF-related cough.

The patients participating in the *FDA's "The Voice of the Patient" (2015)* reported that in addition to cough, the symptoms of shortness of breath and fatigue had the greatest impact on their daily life. Based on this information, and mechanism of action of NAL ER tablets, these additional symptoms may be amenable to treatment and will be investigated with secondary endpoint metrics.

The FDA's "The Voice of the Patient" (2015) mentions that dyspnea is an interchangeable clinical term with breathlessness and describe patients' experience of breathlessness as a symptom, with no distinction in the descriptions being made as to the occurrence of breathlessness with physical activity or breathlessness occurring at rest. The *Bacci et al online supplement (2018)* reports dyspnea in terms of severity of breathlessness with activity and the E-RS breathlessness subscale will be used to analyze whether the concepts of breathlessness associated with or without physical activity can be both or separately affected by NAL ER treatment. The PROMIS fatigue instrument will be used as an additional metric in assessing investigational product efficacy in reducing this burdensome symptom of IPF. There will be an overall clinical assessment of the subject's condition using the Clinical Global Impression of Change instrument.

The study staff, subjects, and Sponsor/clinical research organization (CRO) clinical staff will all be blinded to treatment assignment/sequence to avoid potential bias. Based on titration experience in prior studies in the development program, subjects will have their dose of NAL ER tablets titrated in a blinded manner starting with 27 mg QD up to the target dose of 162 mg BID during the first 2 weeks of active treatment. This titration scheme will increase the likelihood of establishing tolerance to the recognized early side effects of this drug class, mainly in the CNS (dizziness, headache, and somnolence) and gastrointestinal (nausea and vomiting) organ system categories. The target dose of 162 mg BID is within the dose range that was well tolerated in earlier clinical studies of NAL ER tablets.

This study will be conducted in compliance with the protocol and with the International Conference on Harmonisation (ICH) guidelines on Good Clinical Practice (GCP).

6.5 Safety Monitoring

An independent Data Safety Monitoring Board (DSMB) will periodically review safety data. The frequency of data review and DSMB processes are outlined in the DSMB charter.
Subjects will be closely monitored for safety. AEs will be continuously evaluated throughout the study. Vital signs, locally reviewed and central cardiac core laboratory-read ECGs, physical examinations, spirometry, clinical laboratory testing will be conducted to monitor subject safety.

Although nalbuphine is not a controlled substance in the US or the UK, AEs of special interest (AESIs) that code to the most relevant abuse-related Medical Dictionary for Regulatory Activities (MedDRA) preferred terms will be tabulated and descriptive narratives will be written. Additional AEs that are considered "possibly related to abuse potential" will be tabulated separately (the *FDA's "Assessment of Abuse Potential of Drugs: Guidance for Industry" [2017]*). The list of MedDRA preferred terms for AESIs will be described in the statistical analysis plan (SAP).

Subjects will complete the SOWS on a daily basis for 14 days following the last dose of investigational product. Any subjects who are prematurely discontinued from investigational product will also complete the SOWS daily for the 14 days following the last dose of investigational product (unless consent is withdrawn). The SOWS is a self-administered scale for grading opioid withdrawal symptoms and will be collected via the study issued e-diary.

If subjects experience significant withdrawal symptoms during the 2-week safety observation period, they should contact the Investigator. At the Investigator's discretion, they will be offered treatment.

The most frequently reported AEs from NAL ER Phase 1 and 2 clinical studies were primarily in the nervous system and GI organ system categories, consistent with other opiates. The specific AEs that are considered to be expected with use of NAL ER are nausea, vomiting, somnolence, sedation, dizziness, vertigo, and constipation. These are generally mild or moderate in severity and usually resolve over the titration and early dosing period.

To mitigate opioid-related side effects, NAL ER tablets will be initiated with a titration schedule. Titration is a clinical management strategy consistent with dosing of opioids in general (*Jovey et al 2003*). In this study, the combination of a low starting dosing (27 mg NAL ER on the first day) followed by a relatively slow titration is expected to minimize treatment-limiting opioid adverse effects.

It is known from prior studies, that GI adverse effects (e.g., nausea and vomiting) and CNS adverse effects (e.g., dizziness, somnolence, and headaches) occur early and can be treatment-limiting. In anticipation of the possible occurrence of these effects, pre-medications for these symptoms will be permitted.

In anticipation of the possible occurrence of CNS AEs such as somnolence, subjects will be instructed to be aware of possible CNS AEs that may occur. The evening doses during the titration period should be taken at home. The first dose of any new titration step will occur with an evening dose (see instructions for taking study medication). Subjects will be instructed that the investigational product may impair mental and/or physical abilities required for the performance of potentially hazardous tasks such as driving a car or operating machinery, especially during the titration period and in combination with alcohol or tranquilizers or other pharmacologic CNS depressants. Subjects will be instructed not to drive or operate machinery unless they are tolerant to the drug and know how they will react to the medication.

6.6 Risk/Benefit and Ethical Assessment

Nalbuphine has a long history of use in a parenteral formulation, generally for short-term, episodic use related to surgical interventions. The highest dose proposed in the current clinical study is 162 mg BID (324 mg daily dose), well below the highest recommended daily treatment of 144 mg IV dose (equivalent to 864 mg oral dose) for the currently available parenteral administered product. The high peak plasma concentrations that occur in the setting of parenteral use significantly exceed the peak levels observed with NAL ER oral dosing, an observation that is reassuring with respect to the potential for severe, acute toxicity.

Opiate drug class-related concerns such as the potential for physical dependence, linked to longterm use of opiates, is acknowledged. A requirement for completion of a 2-week safety observation period with daily SOWS reporting has been incorporated into the TR12 study. This will facilitate rapid identification and intervention for the respective relevant risks to subjects.

In addition, labeling of opiate-class drugs includes a warning that concomitant use of an opiate together with a benzodiazepine-class drug can increase the risk for respiratory depression, including a risk for respiratory arrest. This warning is based on post-marketing real world data, assessing the experience with a wide range of drugs in these 2 classes and in varied settings including recreational as well as therapeutic usage. In TR12, concomitant benzodiazepine use is not prohibited, and all subjects are informed of this risk through the study Informed Consent Form. At the time of that consent discussion, subjects who are identified as taking a concomitant benzodiazepine should receive the Patient Information Sheet on this topic, as should any subject for whom a concomitant benzodiazepine is subsequently prescribed.

With respect to the published literature addressing respiratory depression with nalbuphine, one relevant study has been identified; which evaluated the respiratory effects of serial intravenous administration of nalbuphine in healthy volunteers. The results were interpreted by the authors as demonstrating a "ceiling" effect for respiratory depression (*Gal et al 1982*). In previous clinical trials with NAL ER, a total of 41 subjects have received concomitant benzodiazepines while receiving NAL ER, and none of these individuals experienced any event of respiratory depression.

In summary, the risk for subjects participating in the TR12 study is judged to be low based on previous experience with oral administration of NAL ER. The current study will utilize a low initiation dose of 27 mg, a gradual dose titration schedule, careful safety monitoring of subjects during the clinical study, and appropriate education of Investigators regarding symptoms of rare but significant AEs linked to the opiate class.

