- 20. Potential subjects cannot have received opiates, including opiate-containing anti-cough agents, within 14 days prior to the screening period. Subjects are prohibited from using opioids, including naltrexone, for the duration of the study.
- 21. Potential subjects cannot currently be receiving benzodiazepines or other CNS Depressant Class Drugs that when used concomitantly with opioids are known to have the potential to cause added pharmacologic effects of depressing CNS activity (See Section 9.6.2.2 ("Benzodiazepines and Other CNS Depressant Class Drugs").
- 22. Potential subjects cannot currently be receiving medications that affect serotonergic neurotransmission and that when used concomitantly with opioids can cause serotonin syndrome (See Section 9.6.2.3 ("Serotonergic Class Drugs").
- 23. Alcohol consumption should be limited for the duration of study treatment (due to the potential cause of added pharmacologic effects of CNS depression when used concomitantly with opioids.
- 24. Change of IPF-related drug treatment regimen within 8 weeks of Screening.

Cardiac-related Exclusions:

- 25. Subjects with a history of congestive heart failure of Class 2 or higher as graded using the New York Heart Association classification (*Appendix 8*).
- 26. Subjects with a history of angina pectoris Grade 2 or higher as graded using the Canadian Cardiovascular Society grading scale (*Appendix 7*).
- 27. History of ventricular tachycardia, Torsade de Pointes, or family history of sudden death.
- 28. Myocardial infarction or acute coronary syndrome within the previous 3 months, as reported by the subject.
- 29. Serum potassium below the laboratory lower limit of normal.
- 30. QTcF interval >450 ms (mean of 3 screening ECG QTcF values) if QRS <120 ms (mean of 3 screening ECG QRS values); QTcF interval >480 ms in the presence of Right Bundle Branch Block (RBBB) and/or QRS ≥ 120 ms
- 31. Heart rate < 45 bpm on any screening measurement. Subjects with a resting heart rate of < 45 bpm will have it repeated once after 5 minutes in the supine position, and if it remains < 45 bpm during the repeat, they will be considered a screen failure.
- 32. Use of a medication having a "known risk" of Torsade de Pointes (categorized as "KR" on the Credible Meds[®] website) is not permitted at entry or during the study (See *Appendix 9*).

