7.4 Withdrawal Criteria

Subjects have the right to withdraw from the study at any time for any reason, without prejudice. At any point, the Investigator may discontinue the subject's study participation at his/her discretion and ensure the subject receives appropriate medical care. The Investigator may consult the Medical Monitor to discuss out-of-range test results. The subject may also be withdrawn at the request of the Sponsor. Additionally, although the Sponsor has every intention of completing the study, the Sponsor reserves the right to discontinue the study at any time and for any reason.

Subjects will be withdrawn from the study for any of the following reasons:

- There is deterioration in the subject's signs and symptoms and/or the subject develops a disease or condition that, in the opinion of the Investigator, would compromise the subject's safety by continuing in the study.
- In the Investigator's judgment, it is in the best interest of the subject.
- There is a violation of the protocol inclusion and/or exclusion criteria, as deemed relevant by the Investigator and discussed with the Medical Monitor.
- The subject withdraws consent for study participation.
- Sponsor terminates the study for any reason.
- Develops a QTcF > 500 ms (mean of 3 ECG QTcF values) in subjects who were randomized without ECG findings of RBBB and/or QRS ≥ 120 ms.
- Develops QTcF > 530 ms (mean of 3 ECG QTcF values) in subjects who were randomized with ECG findings of RBBB and/or QRS ≥ 120 ms.
- Increase from QTcF baseline of > 60 ms (mean determination from 3 ECG values)
- Death of the subject.

If a subject withdraws prematurely from the study during a treatment period due to any of the above criteria or any other reason (unless consent is withdrawn), study staff should make every effort (at withdrawal) to have the subject complete as many of the safety assessments including the SOWS, if possible. The reason for subject withdrawal must be documented in the eCRF. Subjects who withdraw from the study will not be replaced.

If a subject is lost to follow-up, attempts to contact the subject must be made and documented in the subject's eCRF.

If the Sponsor decides to terminate the study, the reason(s) for termination will be documented in the source documents and eCRFs.

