9.6 Concomitant and Prohibited Medications

9.6.1 Concomitant Medications

Subjects may receive all clinically indicated medications during the study with the exceptions noted in *Section 9.6.2 Prohibited Medications* and *Appendix 9*.

Any medication taken by a subject within the 14 days prior to the screening period, and during the course of the study, will be recorded on the eCRF along with the reason for use. During the study,

each subject will be instructed to report the use of all medication, including over-the-counter (OTC) medications, herbal medications, vitamins, and nutritional supplements on the study specific medication log. Sites should instruct subjects to bring the log to each study visit for review. Subjects will also be instructed about the importance of not taking any new medications during the study (including OTC medications) without consulting the Investigator. After screening, if the subject begins taking prohibited or restricted medications, they are to be recorded on the corresponding Concomitant Medication eCRF.

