9.6.2.2 Benzodiazepines and Other CNS Depressant Class Drugs

Because of the potential for an opioid class drug to cause respiratory depression when used concomitantly with other drug classes known to be CNS depressants, the following types of medications are prohibited during the course of the study: sedatives/hypnotics, anxiolytics, tranquilizers, muscle relaxants, general anesthetics, antipsychotics, general anesthetics and antipsychotics. Alcohol is a known CNS depressant and its use should be limited during the course of the study. Please refer to the "Risk from Concomitant Use with Benzodiazepines or Other CNS Depressants" section of the United States Nalbuphine HCl Package Insert (Nalbuphine HCl for injection, for intramuscular, subcutaneous or intravenous use (2016)) for additional information.

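### Protocol 6.6 says benzodiazepines are not prohibited in TR12, contradicting exclusion criterion 21 and the prohibited-medication rule in 9.6.2.2

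*Protocol*

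**What the plan says.** Protocol 6.6 describes the class warning about giving an opiate with a benzodiazepine and then states: "In TR12, concomitant benzodiazepine use is not prohibited, and all subjects are informed of this risk through the study Informed Consent Form". A subject found at the consent discussion to be taking a benzodiazepine is to receive a Patient Information Sheet, "as should any subject for whom a concomitant benzodiazepine is subsequently prescribed". The section adds reassurance from earlier NAL ER trials: "a total of 41 subjects have received concomitant benzodiazepines while receiving NAL ER, and none of these individuals experienced any event of respiratory depression".

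Exclusion criterion 21, in the synopsis and in 7.3, takes the opposite position: "Potential subjects cannot currently be receiving benzodiazepines or other CNS Depressant Class" drugs. It refers the reader to 9.6.2.2. That section belongs to 9.6.2 (Prohibited Medications), has benzodiazepines in its heading and gives respiratory depression as its reason. It says "the following types of medications are prohibited during the course of the study: sedatives/hypnotics, anxiolytics, tranquilizers", and goes on to further classes.

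The default rule is in 9.6.1: "Subjects may receive all clinically indicated medications during the study with the exceptions noted in" section 9.6.2 and Appendix 9.

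All of this is current version 7.0 text. The summary of changes supplied with the protocol (Amendments 5 and 6) does not mention benzodiazepines and so does not reconcile the sections.

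**The concern.** The protocol gives two incompatible rules on a drug combination that it describes as able to cause respiratory depression and arrest, in a population with fibrotic lung disease under blinded dosing. An investigator asked about a new benzodiazepine prescription could rely on 6.6, hand over the information sheet and let the combination continue. Another, reading 9.6.2.2, would treat the same prescription as prohibited.

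The conflict also affects how conduct is recorded. Under 9.6.2.2, on-study use departs from the protocol and goes to the deviation listing and the Minor/Major classification in SAP 4.4.2. Under 6.6 it is not a departure at all. Without a stated governing rule, similar subjects could be classified differently.

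**Working it through.** No alpha, power or sample-size figure is involved. The check compares the texts and then sizes the point.

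**1. Entry and on-study use side by side**

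| Situation | 6.6 | Eligibility and medication sections |
|---|---|---|
| On a benzodiazepine at consent | Not prohibited; give information sheet | Ineligible (exclusion 21) |
| Benzodiazepine prescribed later | Not prohibited; give information sheet | Prohibited (9.6.2.2) |

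The sections conflict in both rows.

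**2. Which text governs.** Section 9.6.1 sends sites to 9.6.2, not to 6.6, to find out what is disallowed. Exclusion 21 points to 9.6.2.2. Section 6.6 is a risk/benefit narrative. The list in 9.6.2.2 does not repeat the word benzodiazepines, but its heading names them, exclusion 21 refers there for them, and the listed classes cover them. The prohibition is therefore the rule to align to.

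**3. How much of 6.6 is wrong.** Only the not-prohibited clause is wrong in itself. Telling all subjects of the risk through the consent form is compatible with a prohibition. So is giving a warning sheet to someone found to be taking a benzodiazepine (9.6.2 itself foresees washout of excluded drugs) or prescribed one later. The sheet misleads only when read with the wrong clause, because the pair then treats use as allowed.

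**4. Window in which a benzodiazepine could be started.** Each period runs from Day 1 to Day 36. If Period 1 Day 36 is also Period 2 Day -1, as 6.3.1 says holds in most instances, the total is 36 + 36 = 72 days. NAL ER is dosed on Days 1 to 22 of one period, so 22 are NAL ER dosing days and 72 - 22 = 50 are placebo or washout days.

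**5. Timing.** SAP 4.15 gives 11 March 2022 as the latest enrolment/randomization date. I take it as the last Day -1 visit.

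- Period 1: Day 1 = 12 March, Day 22 = 2 April, Day 36 = 16 April.
- Period 2: Day 1 = 17 April, Day 22 (last dose) = 8 May, Day 36 = 22 May.
- With the 2-day window used at each follow-up visit: last dose 10 May, final visit 26 May.
- The SAP was signed on 8 June 2022. That is 31 days after the last dose (29 with the window) and 17 days after the final visit (13 with windows).

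SAP section 1 requires the plan to be final at least 1 month before database lock, so lock falls no earlier than about 8 July 2022. SAP 4.4.2 puts the blinded data review meeting shortly before lock. On those rules, deviation classification was still ahead.

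**6. The reassurance in 6.6.** For 0 events in 41 subjects, the exact two-sided 95% upper limit is 1 - 0.025^(1/41) = 0.0860, or 8.6%. This is weak support for permitting the combination, but it is not needed to decide which section governs.

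**The case against.** The strongest reply is that the operative rule is clear. Sites screen from the synopsis and 7.3, and 9.6.1 sends them to 9.6.2. General provisions also cover a benzodiazepine started on study. Subjects are to consult the Investigator before taking new medication; "if the subject begins taking prohibited or restricted medications, they are to be recorded on the corresponding Concomitant Medication eCRF" (9.6.1); under 7.4 "the Investigator may discontinue the subject's study participation at his/her discretion"; and 12.1 says a deviation may lead to withdrawal. Section 6.5 warns subjects about tranquilizers and other CNS depressants, 9.3 allows emergency unblinding, 9.6.2.1 allows an antagonist for urgent reversal, and 10.5 points to overdose guidance.

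This stands as a limit on the likely harm, and it rules out any claim that the protocol is silent on such a case. It does not remove the error. The only instruction specific to a newly prescribed benzodiazepine is in 6.6, and it sits beside a clause saying the use is not prohibited.

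A reader might infer more than the documents support:

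- *That subjects took benzodiazepines with NAL ER in this trial.* The documents give no rate or count of on-study use in TR12.
- *That such use would disappear from the reports under 6.6.* SAP 4.9 records and tabulates all concomitant medications by ATC class and preferred term and plans no separate prohibited-medication table. A benzodiazepine appears either way. The synopsis does promise a summary of prohibited or restricted medications, but the SAP does not carry it forward as its own table.
- *That efficacy results are at stake.* Neither the Full Analysis Set nor the Completers set depends on deviations. Deviation status could bear at most on membership of the Per Protocol Set, on which selected analyses may be repeated for robustness.
- *That both sentences in 6.6 should go.* Deleting them would remove the statement that all subjects are told of the risk, and the direction to warn someone later prescribed the drug.

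**Conclusion.** The contradiction is certain. One clause of 6.6 misstates the rule at entry and on study, and the information-sheet direction inherits the error when read with it. Exclusion 21 and 9.6.2.2 govern. This is an internal inconsistency in a safety instruction and should be corrected.

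Its practical size is limited. On the nominal schedule, no TR12 subject is protected by a change made after May 2022. This assumes that 11 March 2022 was the last randomization date, that the two Visit 6 assessments fell on the same day, and that visits kept to their windows. The number of subjects affected cannot be estimated. What remains for TR12 is consistent deviation classification; for later protocols that reuse the text, it is a correct safety rule. No planned efficacy analysis changes.

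**What to change.** In 6.6, replace the not-prohibited clause with a statement that benzodiazepines are prohibited at entry and throughout the study, citing exclusion criterion 21 and 9.6.2.2. Keep the consent-form disclosure. Keep the information sheet as a warning for any subject found to be taking, or later prescribed, a benzodiazepine. State that such a subject is ineligible at entry or, on study, has a prohibited-medication deviation. Name benzodiazepines in the 9.6.2.2 list. Check that the consent form, which was not available here, states the same rule.

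For TR12 itself, a note recorded before the blinded data review meeting that 9.6.2.2 governs is enough, so that any on-study use is classified as a deviation in the same way for every subject.

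The note costs almost nothing. The text change is one clause and one added statement in 6.6 and one term in 9.6.2.2; if issued as an amendment, it needs ethics committee submission under 13.1. Eligibility, data collection and planned analyses are unchanged. Mandatory contact with the Medical Monitor could be added, but it is optional: the protocol sets no such step for on-study opioids, serotonergic drugs or Torsade-risk drugs, and the contradiction is resolved without it.
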